20 active smokers not treated with ARBs **without** evidence of airflow obstruction by PFT and **normal** DLco but **with** the clinical diagnosis of chronic bronchitis.

Group III, lung healthy, life-time non-smoker:

20 never smokers not treated with ARBs **without** evidence of airflow obstruction by PFT, a **normal** DLco **and no** evidence of the clinical diagnosis of chronic bronchitis

Groups will be appropriately balanced considering COPD stage, smoking status, lung function and age.

Inclusion and Exclusion Criteria

Inclusion criteria

- Age between 35 and 75 years old
- ex-smokers (>10 pack-years of cigarette smoking) not treated with ARBs and with evidence of fixed airflow obstruction by pulmonary function testing (PFT), decreased DLco and with the clinical diagnosis of chronic bronchitis. Or

active smokers (>10 pack-years of cigarette smoking) not treated with ARBs **without** evidence of airflow obstruction by PFT and **normal** DLco but **with** the clinical diagnosis of chronic bronchitis.

Or

never smokers not treated with ARBs **without** evidence of airflow obstruction by PFT, a **normal** DLco **and no** evidence of the clinical diagnosis of chronic bronchitis

• Ability to understand and willingness to sign consent documents

Exclusion criteria:

- Current therapy with ACE inhibitor, intolerance to ARB
- Women of child bearing potential
- Regular use of NSAIDs or potassium supplementation, treatment with aliskiren, anticoagulation
- COPD exacerbation requiring treatment within 6 weeks
- Oral corticosteroid use within 6 weeks
- Significant hypoxemia (oxygen saturation <90% on room air), chronic respiratory failure by history (pCO₂ > 45 mmHg) and forced expiratory volume in 1 second (FEV₁) below 40%, clinical evidence of cor pulmonale

- Untreated arterial hypertension (systolic blood pressure >140 mm Hg, diastolic blood pressure > 90 mm Hg)
- Blood pressure less than 100 mm Hg systolic or 70 mm Hg diastolic at Screening visit and Visit 2.
- Cardiac, renal, hepatic (LFTs > 3x normal upper limit), neurological, psychiatric, endocrine or neoplastic diseases that are judged to interfere with participation in study
- History of renal artery stenosis
- Concomitant airway disorders other than COPD and chronic bronchitis, such as bronchiectasis and asthma (history and reversible airflow obstruction by ATS criteria)
- History of pulmonary malignancies, and any other malignancies in the last 5 years
- History of thoracic surgery.

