- Acute pulmonary exacerbation within 6 weeks from the Screening Visit.
- Subjects with no airflow obstruction by spirometry but with a decrease in DLco < 70% possibly indicating emphysema.
- Significant exposure to environmental tobacco smoke or atmospheric or occupational pollutants for the non-smokers group.
- Urine pregnancy positive test at the Screening Visit.

Treatment arms

Patients will be given four weeks of 50 mg of losartan daily and consequently an additional four weeks of 100 mg of losartan (divided in two doses of 50 mg twice daily). This higher losartan dose was used safely in other clinical trials (www.clinicaltrials.gov; search: losartan and COPD). At the end of each four-week period, participants will be re-evaluated. We will compare treatments using baseline measurements of each individual as his/her own control.

Study Drug:

Cozaar[®], the commercial form of losartan will be obtained from the UMHC Pharmacy and given to the subjects by the PI or study coordinators free of charges. FDA has granted IND exemption for this study. Study drug will be stored as per package instructions in a locked cabined on the research room at UMH 6th floor west room 607. Only the study team has access to this room. The storage area at the study center will be monitored by the staff for temperature consistency with the acceptable storage conditions.

The Investigator is responsible for maintaining accurate study drug accountability records throughout the study.

Each dispensing of study drug will be documented in the subject's study records and in the drug accountability log. Subjects will return all unused study drug for drug accountability. Study drug will be destroyed at the clinical site as per the Institution regulations.

Study Procedures

Once informed consent is signed, the subjects will have an initial visit during which they will have a physical exam (including vital signs), complete study questionnaires and PFTs. All study subjects will undergo the following procedures during a single visit:

History and physical examination will be performed including vital signs and body mass index (BMI) will be recorded.

Laboratory Samples: Urine will be collected for a pregnancy test if applicable and blood test for CMP and CRP will be drawn, if results are not available within 6 months of the Screening visit.

Urine cotinine levels will be measured at the time of study visits to assess smoking status (active or not).

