NPD measurement will be performed according to standard procedures. In this aim, we will use one side of the nose for the evaluation of the function of CFTR and CaCC by measuring the potential differences by initial blocking ENaC with amiloride, then using chloride free solution and isoproterenol to evaluate CFTR function, followed by ATP to evaluate CaCC function. In the other nostril, the same experiment will be repeated as mentioned above, except that after blocking ENaC with amiloride and perfusion with chloride-free solution the CFTR will not be stimulated with isoproterenol, but ATP will be used to maximize the CaCC signal. We will adjust the way of measuring the NPD for aim 2.2 depending of the results in aim 2.1.

TGF-ß and citokines will be measured using Leukosorb, a noninvasive sampling method of the nasal mucosa as previously reported. In addition, we will obtain a small amount of nasal epithelial cells to measure TGF-ß by qPCR.

Study Visits:

V1 (Screening Visit): This will be a single visit for the purpose of determining eligibility, obtaining informed consent, and recording the necessary data will include:

- Assessment of general health status and physical examination (incl. vital signs)
- Urine pregnancy test if indicated (female, child bearing age)
- Spirometry pre- and post-bronchodilators, DL_{co}, lung volumes
- Pulse oximetry
- Review of laboratory values, or if not available: venous blood sampling to assess for renal and liver abnormalities (then the measurements will be done within a week in an additional visit), CRP
- If inclusion criteria fulfilled and no exclusion criteria found:
 - Enrollment

- Completion of respiratory questionnaires (COPD only)
- Six minute walk test (COPD only)
- BODE index calculation

V2 (week 4): This visit (and the two following ones) will only done for the groups not treated with any ARBs. This visit will occur 4 weeks (\pm 4 days) after V1.

- We will again review laboratory values (CMP, CRP), repeat urine pregnancy test if indicated (female, child bearing age).
- The following procedures will be executed:
 - Completion of respiratory questionnaires (COPD only)
 - Six minute walk test (COPD only)
 - BODE index calculation
 - NPD measurement followed by nasal fluid recovered by Leukosorb filter paper and nasal cell collection for TGF-ß

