 - Subjects will be provided with a 4-week supply of 50 mg losartan for daily use (first dose given in clinic; observation with blood pressure monitoring for 2 hours).

V3 (week 5 ± 4 days):

Telephone visit to follow up on symptoms and tolerability of medication.

V4 (week 8 ± 4 days):

- The following procedures will be executed:
 - Monitor for adverse events.
 - Completion of respiratory questionnaires (COPD only)
 - Six minute walk test (COPD only)
 - Venous blood sampling to assess for renal and liver abnormalities and CMP, CRP
 - Urine pregnancy test (if applicable)
 - BODE index calculation
 - Nasal fluid recovered by Leukosorb filter paper and nasal cell collection for TGF-ß
 - Subjects will be provided with a 4-week supply of 50 mg losartan for twice daily use (100 mg)

V5 (week 9 ± 4 days):

Telephone visit to follow up on symptoms and tolerability of medication.

V6 (week 12 ± 4 days) or Early Termination Visit:

- We will draw laboratory (CMP, CRP). Repeat pregnancy test if indicated (female, child bearing age).
- The following procedures will be executed:
 - Monitor for adverse events.
 - Completion of respiratory questionnaires(COPD only)
 - Venous blood sampling to assess for renal and liver abnormalities and CMP, CRP
 - Urine pregnancy test (if applicable)
 - Six minute walk test (COPD only)

- BODE index calculation
- NPD measurement followed by nasal fluid recovered by Leukosorb filter paper and nasal cell collection for TGF-ß

Unscheduled visit (up to 2 visits) will apply if there is a need to repeat study procedures.

Subjects are allowed to be re-screened one time as per PI discretion.

Specimen Banking

Not applicable.

Data Management

Data collected will include demographics, clinical symptoms, health-related quality of life, and pulmonary function test data. Samples to be collected include NPD measurement followed by nasal fluid and cell collection for TGF-ß. We will obtain blood for safety reasons (liver and renal function) and for evaluation of an inflammatory marker. No personal identifiers will be collected and each patient's data will be coded.

Safety Reporting

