Appendix I

	For all	For subjects who are not on ARBs treatment				
	subjects					
	Visit 1 Screening	Visit 2 ^g 4 weeks (± 4 days) after V1	Visit 3 Phone Call 1 weeks (± 4 days) after V2	Visit 4 8 weeks (± 4 days) after V2	Visit 5- Phone Call 9 weeks (± 4 days) after V2	Visit 6 12 weeks (± 4 days) after V2
Informed Consent	X					
Assessment of health status	X	Х		Х		Х
Medical History	Х					
Occupational history	Х					
Smoking History	Х					
Concomitant medication	X		Х		Х	
Urine cotinine test	Х	Х		Х		X
AE and SAE		Х	Х	Х	Х	X
Physical exam	Х	Х		Х		Х
Vital signs	X	X		Х		Х
Urine pregnancy test ^a	Х	Х		Х		Х
β–HGC ^b	Х	X		Х		X
Complete Pulmonary function test pre and post	X					
Renal and liver blood test ^c	X	X		Х		X
CRP ^d	Х	Х		Х		X
Respiratory Questionnaires ^e	X	X		Х		X
6 Minute Walk Test ^f	Х	Х		Х		X
NPD measurement		Х		Х		Х
Nasal fluid for TGF -β measurement	X	Х		Х		Х
Drug Dispensation (losartan 50 mg or 100 mg)		Х		Х		
Drug Compliance				Х		Х

a- Only for female

b- If urine pregnancy test is positive

c- Only if results are not available on the last 6 month

d- Only if results are not available on the last 6 month

e- Respiratory Questionnaire (BCSS, MRC, Charlson co-morbidity index, SGRQ, CAT) will be performed at each visit before any study procedure (COPD group only)

f- 6MWT will be performed for participants on the COPD group only

g- Visit 1 and 2 could be combined if the subject is not on ARBs treatment and has renal and liver blood test results available on the last 6 month.

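### No CRP sample is required in every subject before the first losartan dose, so the own-control CRP baseline can be a chart value up to 6 months old, and Appendix I contradicts the visit text on CRP at V4 and V6

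*Combined protocol and SAP*

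**What the plan says.** **Before the first dose**
- Study Procedures, Laboratory Samples: a "blood test for CMP and CRP will be drawn, if results are not available within 6 months of the Screening visit".
- Study Visits, V1: "Review of laboratory values, or if not available: venous blood sampling to assess for renal and liver abnormalities", with CRP in the same item.
- Study Visits, V2, where the first losartan dose is given: "We will again review laboratory values (CMP, CRP"). The text orders no draw.
- Appendix I marks CRP at V2, but footnote d waives it when a result from the past 6 months exists. Footnote g adds that "Visit 1 and 2 could be combined if the subject is not on ARBs treatment" and has recent renal and liver results. It does not ask for a CRP.

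**On treatment**
- Study Visits, V4: "Venous blood sampling to assess for renal and liver abnormalities and CMP, CRP". V6: "We will draw laboratory (CMP, CRP"). Neither visit text contains a waiver.
- In Appendix I, footnote d is attached to the whole CRP row, which includes V4 and V6.

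**Role of CRP and the comparison**
- Data Management: "We will obtain blood for safety reasons (liver and renal function) and for evaluation of an inflammatory marker".
- Treatment arms: each subject's baseline serves as his or her own control. All groups that go on to V2 receive losartan, so there is no untreated comparator.
- Exclusion criteria: "COPD exacerbation requiring treatment within 6 weeks", and a second item that counts 6 weeks from the Screening Visit.
- Assessment of efficacy is marked not applicable, and Statistical analysis names neither CRP nor a CRP baseline.

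**The concern.** An own-control comparison needs the before and after values to be obtained in the same way. Here the before value may be whatever CRP is in the chart, with no rule on why it was ordered or which laboratory ran it. The after values, if the visit text is followed, are study samples taken at fixed times.

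Two things follow. A longer gap and a possible change of laboratory add variance to the CRP change, which matters in a COPD group of 10. Also, the 6-week exacerbation exclusion covers only a small part of the 6-month chart window. If chart tests tended to be ordered during illness, CRP would appear to fall on losartan with no drug effect, and no untreated arm would reveal it.

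The contradiction in Appendix I is a separate problem: a site that follows footnote d could take no CRP on treatment at all.

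**Working it through.** The documents state no sample size, SD, alpha or effect size for CRP, so there is no plan figure to reproduce. The check is date arithmetic plus an illustration on assumed inputs.

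**1. Share of the chart window outside the exacerbation exclusion.** Six months is 182.6 days, and 182.6/7 = 26.1 weeks. The exclusion covers 6 weeks. (26.1 − 6)/26.1 = 0.77, about 20.1 weeks. This is a share of calendar time, not a probability that a value was raised.

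**2. Greatest age of the CRP at first dose.** The 6 months run back from Screening. V2 follows V1 by 4 weeks ± 4 days, at most 32 days. 182.6 + 32 = 214.6 days, or 30.7 weeks. If footnote d is applied afresh at V2, or V1 and V2 are combined, the limit is 6 months.

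**3. Footnote d read literally at V4 and V6.** Take a subject whose CRP was drawn at V1.
- Visit text, V6 at week 12 ± 4 days: 12 × 7 + 4 = 88 days old at most.
- Appendix I, V6 at 12 weeks ± 4 days after V2: 32 + 88 = 120 days old at most.

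Both are below 182.6 days. The V1 value would satisfy the footnote at every later visit, so no on-treatment CRP would be required. The visit text requires one at V4 and V6. The two cannot both be followed.

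**4. Possible size of a directional bias (all inputs assumed).** Let q be the share of subjects using a chart value, f the share of those values taken when CRP was raised, and m the fold elevation. With no drug effect, mean log baseline is too high by q·f·ln(m), so the geometric mean ratio (on treatment/baseline) is m^−(q·f).

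| q | f | m | q·f | Ratio | Apparent change |
|---|---|---|---|---|---|
| 25% | 10% | 3 | 0.025 | 0.97 | −2.7% |
| 50% | 20% | 3 | 0.10 | 0.90 | −10.4% |
| 100% | 20% | 3 | 0.20 | 0.80 | −19.7% |
| 100% | 30% | 5 | 0.30 | 0.62 | −38.3% |

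The factor q matters because subjects with no result in the window are sampled at screening and carry no chart value.

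**5. Effect on a test (assumed).** This used a paired t-test on log CRP, two-sided 5% (2.5% for a false fall), a within-person log SD of 0.6, and 20,000 simulated trials per case. In the second row of the table, a false fall is declared in 4.9% of trials at n = 10 (the size of Group I) and about 8.6% at n = 30 (the treatment-phase number in Recruitment Methods). Across q = 25–100%, f = 10–30% and m = 3–5, the rates run from 2.8% to 20.8% at n = 10 and from 3.6% to 62.0% at n = 30. The upper ends need every subject to have a chart value and 30% of those to be raised 5-fold.

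**The case against.** The strongest reply is that this concerns a marker with no planned analysis. The objective is NPD, CRP is not a named endpoint, and the own-control sentence is general. NPD and nasal TGF-ß are collected at V2, so the main comparison is untouched. This stands, and it sets the severity.

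A reader might go further and infer that CRP will be biased in losartan's favour. The documents do not support that, for four reasons.
- They do not say how many subjects have a chart CRP or why it was ordered. If the reasons were unrelated to illness, old values would mainly add noise.
- It is tempting to call the on-treatment values exacerbation-free because an exacerbation is a reason for withdrawal. But V6 doubles as the Early Termination Visit, and discontinued subjects are asked to undergo the V6 procedures, which include CRP. A value taken after an exacerbation would push towards a rise and partly offset any fall. Removal of Subjects from Study also lists only severe exacerbations as mandatory, and no stated rule screens other illness out of the on-treatment values.
- The COPD group cannot be assumed the most exposed. Recruitment Methods takes smokers and never-smokers from pre-operative clinics, where recent blood results are also plausible.
- V4 and V6 values cannot simply be called fresh, since footnote d says otherwise.

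What the reply does not remove is the gap itself: no section guarantees a CRP sample before dosing in every subject, and Appendix I and the visit text disagree about CRP afterwards.

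**Conclusion.** The point holds as a minor one. The plan allows a CRP baseline that is not comparable with the on-treatment values: up to 6 months old, or about 31 weeks under the Laboratory Samples wording. It also contradicts itself on whether CRP is measured at V4 and V6.

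The added noise follows from the design. A bias towards a fall is possible but not shown. It rests on the assumption that chart values come disproportionately from illness. Under the middle assumptions (half of subjects with a chart value, 20% of those raised 3-fold) the ratio with no drug effect is 0.90; it reaches 0.80 only if every subject uses a chart value. The NPD objective is not affected.

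**What to change.** - Draw CRP at V2 before the first dose in every subject, including when V1 and V2 are combined, in the same laboratory as V4 and V6. Define this as the only CRP baseline.
- Limit the 6-month allowance for CRP to screening review.
- Reconcile footnote d of Appendix I with the V4 and V6 visit text so that CRP is measured at both visits.
- State that CRP is analysed on the log scale.

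The cost is one CRP sample at V2, where Appendix I already marks CRP, for each subject who would otherwise have relied on an existing result. The text changes are a line each in Laboratory Samples, the V2 text, footnote d and Statistical analysis. This removes the stale-baseline error. It does not remove ordinary fluctuation in CRP or supply the missing untreated arm.

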Treatment with losartan: Cozaar ® is an FDA-approved ARB widely prescribed for treatment of hypertension, heart failure, and for renal protection in patients with diabetes. The doses proposed in this study are well tolerated by non-hypertensive patients without significant effect on blood pressure. The most common side effects are fatigue and dizziness. Serious adverse events that are rare include angioedema, hypotension, renal dysfunction or failure, blood dyscrasias, hepatitis, or rhabdomyolysis (clinical assessment of muscle pain). The following should lower the risks to the subjects: The first dose of medication will be administered in the clinic and the patient observed for two hours with blood pressure monitoring every 30 minutes. If systolic blood pressure falls below 100 mmHg, the patient will be discharged from the study and dosing not repeated.

If the patient has symptomatic hypotension, the patient will be put into a supine position until recovered. If needed additional interventions will be undertaken (including button limited to fluid administration) according to the supervising physician's instructions.

Subjects with hyperkalemia, renal dysfunction, or who are taking potassium supplements will not be enrolled into the study. Participants will be given at the screening visit written descriptions of potential side effects and participants will be instructed to contact the study doctor if any new symptoms occur. Skin rashes, palpitations or other moderate or severe adverse events (interference with usual daily activities) without other clear explanation should warrant immediate cessation of treatment and notification of study personnel.

Six Minute Walk Test: the participant walks for six minutes and the distance traveled is measured. As with any exercise test, there is a theoretical risk but in multiple clinical trials conducted at our site, we had no adverse events. Risks are minimized by medical supervision and trained medical personnel.

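### The plan does not clearly require a fresh metabolic panel before the first losartan dose, so the potassium, renal and liver entry checks can rest on a result 6 to 7 months old

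*Combined protocol and SAP*

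**What the plan says.** Four places in the protocol govern blood tests before the first dose.

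- Study Procedures, Laboratory Samples: "blood test for CMP and CRP will be drawn, if results are not available within 6 months of the Screening visit".
- Study Visits, V1: "Review of laboratory values, or if not available: venous blood sampling to assess for renal and liver abnormalities". Review and sampling are alternatives here.
- Study Visits, V2: "We will again review laboratory values (CMP, CRP". No draw is listed. The first 50 mg dose is given in clinic at this visit.
- Appendix I marks the renal and liver test and CRP at V1, V2, V4 and V6. The rows carry the notes "c- Only if results are not available on the last 6 month" and "d- Only if results are not available on the last 6 month". Footnote g adds: "Visit 1 and 2 could be combined if the subject is not on ARBs treatment and has renal and liver blood test results available", with the same 6-month limit.

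The entry rules that depend on these tests are in two places. Under Risks to Subjects, Treatment with losartan: "Subjects with hyperkalemia, renal dysfunction, or who are taking potassium supplements will not be enrolled into the study". The exclusion criteria add renal disease, and hepatic disease with liver tests above three times the upper limit, where judged to interfere with participation. The same risk section states: "Serious adverse events that are rare include angioedema, hypotension, renal dysfunction or failure".

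After the first dose, V3 is a telephone call. V4 lists venous sampling without condition and dispenses the 100 mg daily supply. V6 also lists a draw without condition.

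**The concern.** Losartan is started in people for whom raised potassium or impaired renal function is meant to be a bar to entry. Whether a subject passes that bar depends on a blood result, and the plan does not clearly say that the result must be recent. A subject whose potassium, creatinine or liver tests became abnormal after the last result on file could be enrolled and dosed in full compliance with the protocol. The first scheduled chance to find this is V4, the visit at which the dose is doubled.

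The plan does refresh other safety criteria before dosing. The blood pressure limits apply at both Screening and V2, and the pregnancy test is repeated at V2 where indicated. The laboratory criteria are the exception.

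**Working it through.** The plan states no figure for the age of the result at first dose, so there is none to reproduce. The check is a reading of the laboratory text plus date arithmetic. Two assumptions are made: 6 months is 183 days, and CMP is the metabolic panel that includes potassium, creatinine and liver tests.

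**Step 1: does the V2 text order a draw?** The V2 line speaks of review. V4 speaks of venous sampling and V6 of drawing. V1 treats review and sampling as different things. The natural reading is that V2 review can be met with a result already on file.

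**Step 2: does Appendix I order a draw at V2?** There are two readings.

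- *Footnotes c and d apply to the whole row.* The V2 test is then waived if a result from the last 6 months exists. Read literally, the notes would also reach V4 and V6. By the visit text, V4 falls at most 56 + 4 = 60 days after V1, and V6 at most 84 + 4 = 88 days. By the Appendix I column headings, V2 falls at most 28 + 4 = 32 days after V1, V4 at most 32 + 60 = 92 days, and V6 at most 32 + 88 = 120 days. All are below 183, so a draw at V1 would waive every later one. That conflicts with the unconditional draws in the V4 and V6 text.
- *Footnotes c and d apply to V1 only.* This fits the Laboratory Samples paragraph, which ties the window to Screening, and it fits V4 and V6. The V2 mark is then an unwaived test.

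**Step 3: does footnote g settle it?** It makes the combined visit conditional on an existing renal and liver result. That condition is needed only if the existing result supports the decision to dose. Footnote g does not mention CRP, which remains under footnote d.

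**Step 4: oldest accepted result at first dose.**

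- V1 and V2 combined under footnote g: 183 days (6.0 months).
- Separate V2, with footnote c counted back from V2: 183 days.
- Separate V2, with the window counted from Screening: 183 + 28 + 4 = 215 days, and 215 / 30.44 = 7.1 months.
- Footnotes c and d limited to V1, separate V2: a draw on the day, age 0. Even then, no text says that the result must be seen before the dose is given.

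**Step 5: first dose to the first scheduled on-drug blood test (V4).**

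- By the visit text (week 4 to week 8): 56 − 28 = 28 days. With 4 days either way at each visit, the range is 20 to 36.
- By the Appendix I column heading (8 weeks after V2): 56 days, range 52 to 60.

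**The case against.** The strongest reply is that Appendix I does mark both tests at V2, and that the reading which best reconciles the document confines footnotes c and d to V1. A site working that way would draw blood at V2. This stands in part: for a separate V2, the gap is one of ambiguity and not of clear permission. It does not remove footnote g, nor the V2 text that asks only for review.

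A second reply is that the plan has other protections. It excludes ACE inhibitors, aliskiren, regular NSAIDs, potassium supplements, renal artery stenosis and low blood pressure. V2 includes an examination and vital signs, the first dose is followed by two hours of observation, and a symptom call comes a week later. These do lower the risk. None of them measures potassium or creatinine.

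A third reply is that 6 months is a deliberate limit and that the documents contain no shorter standard. That is true, and how old a result may be is a clinical judgement. But counting from Screening lets the plan exceed its own 6 months at a separate V2.

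A reader might go further than the text allows in three ways.

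- *That no subject is tested before V4.* Subjects without a result in the window are drawn. The supportable statement is that no draw before V4 is clearly unconditional, and that none is scheduled between first dose and V4.
- *That an old result biases the efficacy or CRP analysis.* No CMP or CRP change is a named endpoint, and the Statistical analysis section specifies no such comparison. The NPD baseline is measured at V2. The documents give neither direction nor size for any bias.
- *That the V4 and V6 draws are waived.* Only a literal reading of the footnotes gives this, and the visit text contradicts it.

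**Conclusion.** The point holds as a safety and eligibility matter. Followed as written, the plan can allow a first losartan dose when the latest potassium, renal and liver results are about 183 days old, or up to about 215 days if the window runs from Screening and V2 is separate. The next scheduled blood test comes about 4 weeks after the first dose by the visit text, or about 8 weeks by the Appendix I heading.

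This rests on taking review at V2 at face value and on footnote g, which is explicit for the combined visit. For a separate V2 it also depends on how footnotes c and d are read. The documents do not say how many subjects would enter on an existing result, so the number affected could be anywhere from none to all of those dosed. The expected harm cannot be calculated. The change is worth making because it is cheap and the entry criteria depend on these tests.

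**What to change.** - At V2, replace the review line with a CMP and CRP draw in every subject, and require potassium, creatinine and liver tests to be reviewed before the first dose. Name this CRP as the pre-dose reference value.
- If same-day results are not possible, draw in the week before V2. The V1 text already foresees an additional laboratory visit within a week.
- Limit footnotes c and d to V1, so that they no longer conflict with the V4 and V6 draws.
- Allow the footnote g combination only when a result from this pre-dose draw is in hand.

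The cost is one extra tube for each dosed subject who has a prior result, at a visit where both tests are already marked, plus edits to three footnotes and one V2 line. Recruitment Methods plans 30 subjects in the treatment phases, while the group sizes add to 10 + 20 + 20 = 50. Withdrawn subjects are replaced, so the number dosed could exceed either figure. The real burden is that screening and dosing on one day becomes harder. The change closes the pre-dose gap only and adds no blood test between first dose and V4.
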